5.6. Part D (JTX-2011 in Combination with Nivolumab Combination Phase 2)

Part D will include approximately 15 subjects in each of 6 dose expansion cohorts (90 total subjects) in the indications listed below of JTX-2011 in combination with nivolumab at a JTX-2011 dose of 0.3 mg/kg:

q3w JTX-2011 + q3w nivolumab

- D01: HNSCC that has progressed on or after a prior PD-1 inhibitor
- D02: NSCLC that has progressed on or after a prior PD-1 inhibitor
- D03: TNBC
- D04: Melanoma that has progressed on or after a prior PD-1 inhibitor (*closed to enrollment*)
- D05: Gastric cancer or gastroesophageal junction adenocarcinoma
- D06: MSI-H or dMMR endometrial cancer (*closed to enrollment*)

The JTX-2011 dose in Part D is 0.3 mg/kg. Subjects in Part D expansion cohorts D01, D02, D03, D04, and D05 will be stratified based on ICOS expression by IHC in archival tumor, with ICOS levels confirmed on a fresh pre-treatment biopsy. At least 10 subjects with high (2+ to 3+) ICOS expression will be enrolled in each 15-subject cohort to explore potential correlation between pre-treatment ICOS expression and efficacy. More subjects may be enrolled to ensure a minimum 10 subjects with high ICOS expression. Additional potential predictive biomarkers will also be evaluated.

Fresh pre-treatment biopsies will be examined retrospectively to assess correlation of potential predictive biomarkers with efficacy.

5.7. Part F (JTX-2011 in Combination with Ipilimumab Phase 2)

Part F will include two (2) cohorts in the indications listed below (approximately 15 subjects each in cohorts F61-F62 (approximately 30 subjects), dosing JTX-2011 in combination with ipilimumab. The JTX-2011 dose level in Part F will be determined in Part E.

[figure not shown]
q6w JTX-2011 + up to 4 doses of Ipilimumab (q3w)

- F61: mCRPC that has progressed on or after treatment with at least one prior standard of care therapy;
- F62: Unresectable or metastatic melanoma with ≤ 2 prior lines of therapy in the unresectable or metastatic setting.

Pre-screening for ICOS will not be required. Subjects in Part F are required to have archival tumor and two fresh tumor biopsies (one during screening and one post-dose between C2D1 and C2D22). In situations where archival tissue is not available or biopsies are not feasible (e.g., would expose the subject to unreasonable health risks), one or more of these requirements may be waived after discussion with the Medical Monitor.

To complete enrollment in the Part F cohorts, at least 15 assessable pre-treatment fresh biopsies must have been obtained in each cohort.

Figure 8: Part F Treatment Schema

5.8. Part H (JTX-2011 in Combination with Pembrolizumab Combination Phase 2)

Part H will include six (6) cohorts in the indications listed below, dosing JTX-2011 at q3w in combination with pembrolizumab in Cohorts H31-H35 and q6w in combination with pembrolizumab in Cohort H64. Approximately 15 subjects will be enrolled in Cohorts H31-H33 and H35. Cohorts H34 and H64 are expansion cohorts and will each enroll approximately 49 subjects. All subjects must be immunotherapy naïve:

q3w JTX-2011 + q3w Pembrolizumab

- H31: recurrent or metastatic HNSCC with disease progression on or after platinum-containing chemotherapy;
- H32: metastatic NSCLC that has high PD-L1 expression (TPS Score $\geq 50\%$) as determined by an FDA-approved test, with no EGFR or ALK genomic tumor aberrations;
- H33: metastatic or recurrent TNBC with ≤ 1 prior line of therapy in the metastatic or recurrent setting;

- H34: recurrent locally advanced or metastatic gastric or gastroesophageal junction adenocarcinoma, including adenocarcinoma of the lower esophagus with disease progression on or after 1 prior line of therapy, including HER2/neu-targeted therapy, if appropriate;
- H35: unresectable or metastatic MSI-H solid tumors that have progressed on prior FDA-approved treatment and who have no satisfactory alternative treatment options or MSI-H colorectal cancer that has progressed following treatment with a fluoropyrimidine, oxaliplatin, and irinotecan.

q6w JTX-2011 + q3w Pembrolizumab

- H64: recurrent locally advanced or metastatic gastric or gastroesophageal junction adenocarcinoma, including adenocarcinoma of the lower esophagus with disease progression on or after 1 prior line of therapy, including HER2/neu-targeted therapy, if appropriate

Pre-screening for ICOS will not be required. Subjects in Part H are required to have archival tumor and a fresh tumor biopsy during screening. In situations where archival tissue is not available or biopsies are not feasible (e.g., would expose the subject to unreasonable health risks), one or more of these requirements may be waived after discussion with the Medical Monitor.

To complete enrollment in the HNSCC (H31), NSCLC (H32), TNBC (H33), and MSI-H solid tumor (H35) cohorts, at least 15 assessable fresh biopsies must have been obtained in each cohort, 10 of which must have an ICOS score ≥ 1 . To complete enrollment in the gastric expansion cohorts (H34 and H64), approximately 49 assessable fresh biopsies must be obtained in each, 33 of which must have an ICOS score of ≥ 1 .

Figure 9: Part H q3w Treatment Schema

[figure not shown]
[figure not shown]

Figure 10: Part H q6w Treatment Schema

6. DOSE ESCALATION, MODIFICATION, AND PATIENT WITHDRAWAL

6.1. Safety Monitoring Committee

6.1.1. Dose Escalation

A Safety Monitoring Committee (SMC) composed of Investigators, study staff, Medical Monitor, and Sponsor representatives will review and approve all dose escalation decisions in Parts E and G. Dose escalation in Parts A and B have been completed with a recommended RP2D of 0.3 mg/kg q3w in both parts.

The SMC will review, at a minimum, the following safety data:

- Vital signs
- Clinical laboratory values
- Physical examination findings
- Adverse events/serious adverse events
- ECOG performance status

The SMC will hold a teleconference prior to dose escalations in Parts E and G. Based on the review of the data, the SMC will recommend that the study continue with escalation to the next dose, that an additional three subjects be enrolled at the current dose, or may alternatively recommend that the study be placed on hold, that the dose of study drug be de-escalated, or that the study be terminated. A recommendation of study hold, study drug dose de-escalation, or study termination would be made in the event of the discovery of an unexpected, serious, or unacceptable risk to the subjects in the study.

In addition, the SMC will review safety data for aggregate AEs for 9 weeks. Based on the review of the data, the SMC will recommend that the study continue as planned, or may alternatively recommend that the study be placed on hold, that the dose of study drug be de-escalated, or that the study be terminated. A recommendation of study hold, study drug dose de-escalation, or study termination would be made in the event of the discovery of an unexpected, serious, or unacceptable risk to the subjects in the study.

6.1.2. Ongoing Safety Review

Once dose escalation has been completed, the SMC will be convened approximately every 3 months to review accumulating safety data and subject disposition by cohort.

6.2. Dose Escalation Scheme

In Part A, six (6) dose escalation cohorts were explored, 0.003 mg/kg, 0.01 mg/kg, 0.03 mg/kg, 0.1 mg/kg, 0.3 mg/kg, and 1 mg/kg. In Part B, four (4) dose escalation cohorts were explored, 0.01 mg/kg, 0.03 mg/kg, 0.1 mg/kg, 0.3 mg/kg.

In Parts E and G, each dose escalation cohort will consist of a minimum of 3 subjects. The first subject in each dose cohort will receive JTX-2011 + ipilimumab or + pembrolizumab, respectively, on CID1 (sentinel subject) and be monitored for at least 72 hours as an outpatient until acute and subacute safety is confirmed. If, after 72 hours, there are no safety concerns, the

next two subjects in the dose cohort will be allowed to enroll in parallel (if the Investigator and Sponsor agree, then no SMC review will be required). Note: hospitalization is not required).

If, after 72 hours, there are no safety concerns, the next two subjects in the dose cohort will be allowed to enroll in parallel (if the Investigator and Sponsor agree, then no SMC review will be required).

The first 3 or 6 subjects at each dose-level will be assigned according to the classical 3 + 3 design, as follows. If:

- 0 of 3 subjects in a cohort experiences a DLT, then the next higher dose-level cohort may be enrolled.
- 1 of 3 subjects in a cohort experiences a DLT, then enrollment into that cohort will be expanded to a total of 6 subjects.
- 1 of 6 subjects in an expanded cohort experiences a DLT, then the next higher dose-level cohort may be enrolled.
- >1 of 3-6 subjects in a cohort experience a DLT, then the MTD has been exceeded and further enrollment into that cohort will cease. Using the same criteria, additional cohorts may then be explored until the MTD has been determined, including intermediate doses.

Subjects in each cohort must complete the first cycle of each cohort through C2D1 assessments or have experienced a DLT to be considered evaluable; non-evaluable subjects will be replaced.

Once a RP2D is determined for a particular part of the trial, subjects at lower doses in that part who remain on study treatment and are tolerating it well may increase their dose to the RP2D. In addition, the SMC will be convened approximately every 3 months to review accumulating safety data and patient disposition by cohort through the duration of the study.

6.2.1. Initiation of Parts C, D, F, and H

Part C

Assuming that there are no safety concerns in Part A, enrollment in Part C will begin once a dose is identified from Part A that results in approximately 70% sustained ICOS TE through day 21 and PK that support dosing q3w or q6w or the MTD is identified. This is anticipated to be one dose level above the dose level selected for Safety/PK/PD Expansion cohort AP1.

Part D

Assuming that there are no safety concerns in Part B, enrollment in Part D will begin once a dose is identified from Part B that results in approximately 70% sustained ICOS TE and PK that support dosing q3w or the MTD is identified. This is anticipated to be one dose level above the dose level selected for Safety/PK/PD Expansion cohort BP1.

Part F

Enrollment in Part F will begin assuming that there are no safety concerns and the RP2D has been determined from Part E.

Part H

Enrollment in Part H will begin assuming that there are no safety concerns and the RP2D has been confirmed from Part G.

6.2.2. Criteria for Proceeding to the Next Dose Level

Depending upon the dosing schedule being tested in dose escalation, the Safety Monitoring Committee (SMC) will review all safety data available through at least 2 weeks (in q3w dosing) or 5 weeks (q6w dosing) and make an initial dose escalation recommendation. Enrollment in the next dose escalation cohort may occur after:

- SMC determines that there are no safety concerns with review of ≥ 14 days data for all evaluable subjects within a cohort;
- All subjects within a dose cohort complete ≥ 1 cycle;
- DLT observed in < 1 out of 3 evaluable subjects (or < 2 out of 6 evaluable subjects) during Cycle 1;
- SMC agrees that no additional subjects are required in the current cohort to further define safety.

Following the review of safety data obtained at a given dose level, the SMC will convene via telephone conferences and decide the dose level for the next cohort. If potential safety signals are identified, the administration of interim dose levels (e.g., increment of $< 25\%$ of current dose level instead of 25-50%) may be recommended. In addition, to enable accurate and appropriate clinical and scientific interpretation of the data, a dose level may be repeated as requested by the SMC. Dose escalation will be recommended only if a consensus to escalate is reached by the SMC after review and discussion of the current dose level's safety data.

6.3. Definition of Dose Limiting Toxicity (DLT)

A DLT is defined as any of the following study drug-related toxicities (defined as at least possibly related to study drug) **occurring in the first cycle** of study treatment:

Hematological:

- \geq Grade 4 neutropenia lasting > 7 days;
- Febrile neutropenia;
- Any Grade 3 thrombocytopenia with bleeding or a requirement for platelet transfusions;
- \geq Grade 4 thrombocytopenia (platelets $< 25,000/\mu\text{L}$).

Non-hematological:

- AST or ALT $> 3 \times$ ULN and concurrent total bilirubin $> 2 \times$ ULN without initial findings of cholestasis (e.g. findings consistent with Hy's law or FDA definition of potential drug-induced liver injury [pDILI]);
- \geq Grade 4 AST or ALT of any duration;
- Any \geq Grade 3 non-hematologic toxicity with the following exceptions:
 - Grade 3 immune-related AE (irAE) that resolves to \leq Grade 1 or to baseline with immunosuppressive therapy within 3 weeks;
 - Grade 3 fatigue that persists < 7 days;
 - Grade 3 rash that resolves to \leq Grade 1 within 3 weeks;
 - Grade 3 or 4 elevation in serum amylase and/or lipase that are not associated with clinical or radiographic evidence of pancreatitis;

- \geq Grade 3 electrolyte abnormality that lasts $<$ 72 hours, is not clinically complicated, and resolves spontaneously or responds to conventional medical intervention;
- Grade 3 nausea or vomiting that lasts $<$ 48 hours, and resolves to \leq Grade 1 either spontaneously or with conventional medical intervention;
- Grade 3 infusion reaction that resolves within 6 hours to \leq Grade 1;
- Alopecia;
- Grade 3 endocrinopathy that is adequately controlled by hormone replacement;
- Grade 3 tumor flare.
- Any Grade 4 or 5 Adverse Event (AE);
- Any Grade 2 drug-related uveitis or eye pain or blurred vision that does not respond to topical therapy and does not improve to Grade 1 severity within 2 weeks OR requires systemic treatment;
- Any treatment-related Grade 2 or greater toxicity that persists and results in an inability to administer C2D1.

For events that are not included in the above definitions, the SMC may declare any additional specific toxicity to be a DLT.

If a subject experiences a DLT which subsequently resolves to baseline and does not automatically meet the criteria for study discontinuation (e.g., Grade 4 AST or ALT), the Sponsor in conjunction with the Investigator and/or SMC, may decide if the subject is allowed to stay on study treatment and resume treatment at a lower dose.

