6.7.3. Dose Modifications

6.7.3.1. Dose Modifications for JTX-2011

During dose-escalation, dose modifications are not allowed during Cycle 1, unless the subject experiences an infusion related reaction during the first administration of JTX-2011 which prevents the patient from receiving the first dose in its entirety. If, during the first dose, a subject experiences an infusion reaction where the Investigator determines the infusion should be terminated prematurely as a safety precaution, the event should be treated as a DLT according to Protocol Section 6.3.

The Investigator should then consult the Jounce Medical Monitor to determine if the patient should be either discontinued from the study, or proceed with future modified infusions (e.g., slower rate, lower dose group). Any AE that is severe enough (at the discretion of the Investigator and with permission of the Sponsor/CRO Medical Monitor) to warrant a dose reduction during Cycle 1 will be considered a DLT.

Dose Modifications and Management of Toxicity for JTX-2011 is provided in Table 5.

Table 5: Dose Modifications and Toxicity Management for JTX-2011, Nivolumab, Ipilimumab and Pembrolizumab

Adverse Event	Severity	Dose Modification	Recommended Management ^a
Diarrhea or Colitis	Grade 2	
Withhold study drug(s) until symptoms resolved to Grade 0-1.
 
If occurring in combination with nivolumab, ipilimumab or pembrolizumab, when symptoms resolved to Grade 0-1, resume JTX-2011. If symptoms do not recur after 1 cycle of JTX-2011, resume combination.^e
 
Permanently discontinue ipilimumab if symptoms last 6 weeks or longer or inability to reduce corticosteroid dose to 7.5 mg prednisone or equivalent per day
	If symptoms persist > 5 days or recur: 0.5 to 1 mg/kg/day prednisone equivalents followed by steroid taper ^a
	Grade 3	
Withhold study drug(s) until symptoms resolved to Grade 0-1.
 
If occurring in combination with nivolumab or pembrolizumab, when symptoms resolved to Grade 0-1, resume JTX-2011. If symptoms do not recur after 1 cycle of JTX-2011, resume combination.
 
Permanently discontinue if in combination with ipilimumab
	1-2 mg/kg/day prednisone equivalents followed by steroid taper ^a
	Grade 4	Permanently discontinue	1-2 mg/kg/day prednisone equivalents followed by steroid taper ^a

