Pneumonitis	Grade 2	
Withhold study drug(s) until resolved to Grade 0-1
 
If occurring in combination with nivolumab, ipilimumab or pembrolizumab, when symptoms resolved to Grade 0-1, resume JTX-2011. If symptoms do not recur after 1 cycle of JTX-2011, resume combination.^e
 
Permanently discontinue study drugs if recurrent grade 2 pneumonitis in combination with pembrolizumab
	1-2 mg/kg/day prednisone equivalents followed by steroid taper ^a
	Permanently discontinue ipilimumab if symptoms last 6 weeks or longer	1-2 mg/kg/day prednisone equivalents followed by steroid taper ^a	

	Grade 3 or 4	Permanently discontinue	1-2 mg/kg/day prednisone taper ^a
Hepatitis	Grade 2 AST/ALT (>3 to 5 x ULN) or bilirubin (1.5 to 3 x ULN) ^b	Withhold study drug(s) until resolved to Grade 0-1. If occurring in combination with nivolumab, ipilimumab or pembrolizumab, when symptoms resolved to Grade 0-1, resume JTX-2011. If symptoms do not recur after 1 cycle of JTX-2011, resume combination. ^c	0.5 to 1 mg/kg/day prednisone equivalents or investigator discretion ^a
	Grade 3 or 4 AST/ALT (>5 x ULN) or bilirubin (>3 x ULN) ^b	Permanently discontinue ipilimumab if symptoms last 6 weeks or longer Permanently discontinue	1-2 mg/kg/day prednisone equivalents or investigator discretion ^a
Hypophysitis	Grade 2 or 3	Withhold study drug(s) until resolved to Grade 0-1 If occurring in combination with nivolumab, ipilimumab or pembrolizumab, when symptoms resolved to Grade 0-1, resume JTX-2011. If symptoms do not recur after 1 cycle of JTX-2011, resume combination. ^c	1 mg/kg/day prednisone equivalents ^a
	Grade 4	If occurring in combination with ipilimumab, permanently discontinue study drugs if symptomatic endocrinopathy lasts 6 weeks or longer or if there's inability to reduce corticosteroid dose to 7.5 mg prednisone or equivalent per day Permanently discontinue if not manageable with medical treatment	1 mg/kg/day prednisone equivalents ^a
Adrenal insufficiency	Grade 2	Withhold study drug(s) until resolved to Grade 0-1 If occurring in combination with nivolumab, ipilimumab or pembrolizumab, when symptoms resolved to Grade 0-1, resume JTX-2011. If symptoms do not recur after 1 cycle of JTX-2011, resume combination. ^c	Observation

		Permanently discontinue study drugs if symptomatic endocrinopathy in combination with ipilimumab lasts 6 weeks or longer or if there's inability to reduce corticosteroid dose to 7.5 mg prednisone or equivalent per day	

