	Grade 4 hyperglycemia	Permanently discontinue if not manageable with medical treatment. Permanently discontinue study drugs if symptomatic endocrinopathy in combination with ipilimumab lasts 6 weeks or longer or if there's inability to reduce corticosteroid dose to 7.5 mg prednisone or equivalent per day	Administer insulin
Nephritis and Renal Dysfunction	Grade 2: serum creatinine (>1.5 to $3 \times$ ULN)	Withhold study drug(s) until resolution to Grade 0-1 If occurring in combination with nivolumab, ipilimumab or pembrolizumab, when resolved to Grade 0-1, resume JTX-2011. If increase in serum creatinine does not recur after 1 cycle of JTX-2011, resume combination. ^c	0.5 to 1 mg/kg/day prednisone equivalents followed by steroid taper. If worsening or no improvement occurs, increase dose of corticosteroids to 1-2 mg/kg/day prednisone equivalents and permanently discontinue. ^a
	Grade 3: serum creatinine (>3 to $6 \times$ ULN)	If occurring with monotherapy or in combination with nivolumab, withhold study drug(s). When resolved to Grade 0-1, resume JTX-2011. If increase in serum creatinine does not recur after 1 cycle of JTX-2011, resume combination, if applicable. Permanently discontinue study drugs if occurring in combination with pembrolizumab or ipilimumab	1-2 mg/kg/day prednisone equivalents ^a
Rash	Grade 4: serum creatinine ($>6 \times$ ULN)	Permanently discontinue	1-2 mg/kg/day prednisone equivalents ^a
	Grade 2	Only if occurring in combination with ipilimumab, withhold study drugs. When symptoms resolve to Grade 0-1, resume JTX-2011. If symptoms do not recur after 1 cycle of JTX-2011, resume combination. ^c	0.5 to 1 mg/kg/day prednisone equivalents ^a

	Grade 3	
Withhold study drug(s) until resolution to Grade 0-1.
 
If occurring in combination with nivolumab or pembrolizumab, when symptoms resolved to Grade 0-1, resume JTX-2011. If symptoms do not recur after 1 cycle of JTX-2011, resume combination.
 
Permanently discontinue if in combination with ipilimumab
 
Permanently discontinue
	1-2 mg/kg/day prednisone equivalents ^a
	Grade 4	Permanently discontinue	1-2 mg/kg/day prednisone equivalents ^a

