Neuropathy	Grade 2	
Withhold study drug(s) until resolved to Grade 0-1; if symptoms persist \geq 6 weeks, subject continuation discussed between PI and Medical Monitor
 
If occurring in combination with nivolumab, ipilimumab or pembrolizumab, when symptoms resolved to Grade 0-1, resume JTX-2011. If symptoms do not recur after 1 cycle of JTX-2011, resume combination.^c
 
If occurring in combination with ipilimumab, permanently discontinue study drugs for related reactions lasting 6 weeks or longer or inability to reduce corticosteroid dose to 7.5 mg prednisone or equivalent per day
	None
	Grade 3	
Withhold study drug(s) until resolved to Grade 0-1; if symptoms persist \geq 6 weeks subject continuation discussed between PI and Medical Monitor
 
If occurring in combination with nivolumab or pembrolizumab, when symptoms resolved to Grade 0-1, resume JTX-2011. If symptoms do not recur after 1 cycle of JTX-2011, resume combination.
 
Permanently discontinue study drugs if occurred in combination with ipilimumab
 
Permanently discontinue
	1-2 mg/kg/day prednisone equivalents ^a
	Grade 4	Permanently discontinue	1-2 mg/kg/day prednisone equivalents ^a

Encephalitis	New-onset moderate or severe neurologic signs or symptoms	Permanently discontinue	If etiologies other than immune-mediated adverse event are ruled out, permanently discontinue JTX-2011 and administer 1-2 mg/kg/day prednisone equivalents ^a
	Immune-mediated encephalitis	Permanently discontinue	1-2 mg/kg/day prednisone equivalents ^a
Ophthalmologic	Uveitis, iritis, or episcleritis	Permanently discontinue if not resolved to Grade 0-1 with local immunosuppressive therapy	Corticosteroid eye drops
	Other Grade 3 adverse reaction	Withhold study drug(s) until resolution to Grade 0-1. If occurring in combination with nivolumab or pembrolizumab, when symptoms resolved to Grade 0-1, resume JTX-2011. If symptoms do not recur after 1 cycle of JTX-2011, resume combination.	Consider 1-2 mg/kg/day prednisone equivalents ^a
Other	Recurrence of same Grade 3 adverse reaction	Permanently discontinue study drugs if occurring in combination with ipilimumab Subject continuation discussed between PI and Medical Monitor	1-2 mg/kg/day prednisone equivalents ^a
	Life threatening or Grade 4 adverse reaction	Permanently discontinue	1-2 mg/kg/day prednisone equivalents ^a
	Requirement for 10 mg prednisone per day or greater prednisone or equivalent for > 12 weeks	Permanently discontinue	

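### The DLT definition exempts quickly resolving Grade 3 immune-related events even when Table 5 ends treatment for them, so such an event can leave the DLT count unless the SMC steps in

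*Protocol*

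**What the plan says.** Protocol 6.3 makes a related non-hematologic toxicity of Grade 3 or worse in Cycle 1 a DLT, with listed exceptions. One is a Grade 3 immune-related event that returns to Grade 1 or less "or to baseline with immunosuppressive therapy within 3 weeks". Another is a Grade 3 rash that returns to Grade 1 or less within 3 weeks. The last listed criterion is "Any treatment-related Grade 2 or greater toxicity that persists and results in an inability to administer C2D1". For events outside the list, "the SMC may declare any additional specific toxicity to be a DLT".

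Table 5 (Protocol 6.7.3.1) sets the treatment consequence for Grade 3 events:

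- Pneumonitis: permanent discontinuation in any part.
- Hepatitis, row "Grade 3 or 4 AST/ALT (>5 x ULN) or bilirubin": permanent discontinuation in any part. The cells run together in the text available, but the row reads this way.
- Nephritis: "Permanently discontinue study drugs if occurring in combination with pembrolizumab or ipilimumab".
- Diarrhea or colitis, and rash: "Permanently discontinue if in combination with ipilimumab".
- Neuropathy: "Permanently discontinue study drugs if occurred in combination with ipilimumab".

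The text of 6.7.3.1 also makes two treatment consequences into DLTs: an adverse event severe enough to warrant a Cycle 1 dose reduction, and an infusion reaction that ends the first infusion early. It does not mention permanent discontinuation.

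Under 6.2 and 6.8.2, a subject who leaves treatment before completing C2D1 assessments is replaced unless a DLT has occurred. SAP 6.1.1 limits the DLT Evaluable Set to subjects who complete the first cycle or have a DLT, and SAP 9.9.1 summarizes DLTs in that set only.

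**The concern.** A DLT count should include toxicity that prevents a patient from continuing. Here a lesser consequence, a Cycle 1 dose reduction, is a DLT by rule, while a greater one, permanent discontinuation, is not named. The protocol already lets a consequence override an exemption: 6.3 excuses a Grade 3 infusion reaction that settles within 6 hours, yet 6.7.3.1 counts a reaction that terminates the first infusion.

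The dose-escalation criterion in 6.2.2 and the MTD definition in 6.6 both rest on the DLT rate. If a related, treatment-ending event removes its subject from that rate, the rate is too low at that dose level, and a reader of the DLT table cannot see why. Safety, tolerability and the MTD are primary objectives of Phase 1.

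**Working it through.** **No plan figure to reproduce.** No sample size, power or error rate in either document depends on this point. The check compares the rules and then gives an illustration.

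**Following one event through the rules.** Take a related Grade 3 pneumonitis in Part G (q3w) that resolves on steroids before C2D1.

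1. 6.3, Grade 3 criterion: exempt, since it resolved on immunosuppression within 3 weeks.
2. 6.3, last criterion: not met, since the toxicity did not persist to block C2D1.
3. Table 5: study treatment ends.
4. 6.7.3.1: a dose reduction would make it a DLT; discontinuation is not stated.
5. 6.2 and 6.8.2: withdrawn before completing C2D1 assessments, no DLT, so replaced.
6. SAP 6.1.1: first cycle not completed through C2D1, no DLT, so outside the DLT Evaluable Set.

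**Limits of the gap.**

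- The exemption requires recovery within 3 weeks; recovery before C2D1 alone is not enough. In Part E (q6w) C2D1 is Day 43. A Grade 3 colitis from Day 8 to Day 36 has resolved before C2D1 but took 28 days, so it is a DLT. An exempt event that starts by Day 22 resolves by Day 22 + 21 = Day 43.
- In q3w parts C2D1 is Day 22, so onset and recovery must both fall within about 21 days.
- Hepatitis with AST or ALT above 3x ULN and bilirubin above 2x ULN, without initial cholestasis, is a DLT under its own criterion however fast it resolves. Grade 4 AST or ALT is also a DLT.

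**Illustration with assumed rates.** Let d be the rate of events already counted as DLTs, r the rate of exempt but treatment-ending events, and s the share of those that the SMC declares DLTs. None of the three is given in the documents. A dose level clears the 3+3 rule with 0 of 3, or with 1 of 3 followed by 0 of the next 3:

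P(clear) = (1−p)³ + 3p(1−p)⁵

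With replacement, p = (d + s·r) / (1 − (1−s)·r). If all such events count, p = d + r.

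For d = 0.10, r = 0.05, s = 0: p = 0.10/0.95 = 0.1053 and P(clear) = 0.897. Counted: p = 0.15 and P(clear) = 0.814. The gap is 0.083.

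| r (d = 0.10) | replaced, none declared | replaced, half declared | all counted |
|---|---|---|---|
| 2% | 0.903 | 0.887 | 0.871 |
| 5% | 0.897 | 0.856 | 0.814 |
| 10% | 0.887 | 0.798 | 0.709 |
| 20% | 0.862 | 0.660 | 0.494 |

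The choice of d matters less. At r = 5% with none declared, the comparison is 0.971 against 0.906 for d = 0.05, and 0.686 against 0.600 for d = 0.20.

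**Effect on a reported rate.** Suppose a dose level has one DLT and one replaced event. The DLT Evaluable Set shows 1/6 = 17%. In all 7 treated subjects, a DLT or such an event occurred in 2/7 = 29%.

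**The case against.** The best defense is that the exemption is deliberate and other provisions cover the rest. Reversible immune-related events are expected with these drugs, and 6.3 treats DLT status and discontinuation as separate matters. An event bad enough to end treatment is arguably more than severe enough to warrant a dose reduction, so 6.7.3.1 covers it by implication. The SMC reviews all available safety data, must find no safety concerns, and escalates "only if a consensus to escalate is reached by the SMC". It may also suspend escalation on other grounds (6.4). Some discontinuation rules follow the partner drug's label, so counting those events would charge fixed-dose ipilimumab toxicity to the JTX-2011 dose.

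Much of this stands. The SMC is a real safeguard, and the clearance probabilities model the DLT count alone, whereas 6.2.2 sets further conditions. Three answers remain. The SMC declaration is permissive, and the no-safety-concerns condition is worded for evaluable subjects, which a replaced subject is not. Coverage through 6.7.3.1 must be inferred, and that rule itself depends on Investigator discretion and Medical Monitor permission. Partner-drug toxicity is not a new trade-off, since 3.6 already includes the combination in the definition of study drug.

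The reporting defense is also partly right. SAP 9.9.1 already shows these events in the Safety Analysis Set, by dose level, among immune-related events by preferred term and cycle and among events leading to discontinuation. What it lacks is a display that sets them beside the DLT rate.

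**Conclusion.** The gap is real, narrow, and of minor to moderate importance. A related Grade 3 immune-related event or rash that meets the 3-week exemption, resolves before C2D1 and ends treatment under Table 5 need not be counted by any listed criterion, and its subject is replaced. Under the assumed 10% and 5% rates with no SMC declaration, clearance is about 0.90 instead of 0.81. If the SMC declares half of such events the gap falls to about 0.04 (0.856 against 0.814), and if it declares all of them there is none.

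Two stronger readings are not supported. A reader might infer that in Part G the subject stays in the cohort as a non-DLT, because an End of Treatment visit (Days 22–36 after a single Day 1 dose) can overlap the C2D1 window (Days 19–25). But 6.8.2 turns on withdrawal from treatment before C2D1 assessments are complete, and the C2D1 visit in 7.2.7 includes dosing, so the subject is replaced. A reader might also infer that the MTD or RP2D is wrong. The documents report no such events, the illustrative 29% is still below the 33% in 6.6, and the RP2D also rests on PK, pharmacodynamics and infusion tolerability.

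SAP Section 4 states that all Phase 1 parts are complete and that Parts F and H never opened. The live consequence is therefore how the DLT rate is reported.

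**What to change.** Add to Protocol 6.3 and 6.7.3.1: any study-drug-related toxicity that requires permanent discontinuation of study drug in Cycle 1 is a DLT, regardless of the listed exceptions. This states outright what the dose-reduction rule implies, and makes the subject evaluable under 6.2, 6.8.2 and SAP 6.1.1 without an SMC declaration.

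For the completed data, add one supplementary display to SAP 9.9.1, by dose level, for Parts A, B, E and G. Show the planned DLT rate in the DLT Evaluable Set. Beside it show, in all treated subjects including those replaced, the rate of a DLT or a Cycle 1 permanent discontinuation for a related adverse event. Flag partner-drug attribution for each added event, and state that the display does not redefine the MTD.

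The cost is one sentence in two protocol sections and one table from data already collected. In any further escalation a cohort may expand to 6, or escalation may stop earlier. Some toxicity driven by the partner drug may count against the JTX-2011 dose; the attribution flag makes that visible in reporting but does not remove it from the count.
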